## 4. P. Assessment of Safety

#### 1. Definition of adverse event.

An adverse event is any untoward medical experience occurring in a subject doing the trial whether or not is related to study drug. An adverse event includes a concurrent illness, injury, or any other aspect of the subject's health, as well as abnormal laboratory findings found to be of clinical significance. An adverse event includes worsening of an existing symptom or condition or post treatment events that occur as a result of protocol – mandated procedures.

An adverse event may be a disease, a set of related symptoms or signs, or single symptom or sign including an abnormal laboratory value.

For the purposes of this trial, all adverse events will be collected including adverse events that occurred subjects were permanently off of study drug but who continue to be followed for outcomes.

A serious adverse event is an adverse event occurring any does that results in any of the following, whether or not it is related to study drug: death, immediately life-

threatening circumstance, inpatient hospitalization or prolongation of existing hospitalization, a persistent or significant disability.

Life-threatening means that the subject in the view of the investigator was thought to be at immediate risk of death from the event as it occurred.

Serious events will be collected, including serious adverse events occurring when subjects were permanently off study drug but who continue to be follow-up for outcomes.

#### 2. Unanticipated problems.

An unanticipated problem is any incident, experience, or outcome involving risk to subjects that meets all of the following criteria: unexpected in nature, severity or frequency; related or possibly related to participation in the research; and suggests that the research places subjects or others at a greater risk of harm.

#### 3. Relatedness or causality.

Causality is defined as definitely, probably, possibly or not related to the investigational product:

- Not related, event clearly related to other factors

 Possibly related, sequence of events is compatible with study procedure but could have been produced by other factors

 Probably related, sequences of events that is compatible with study procedure that cannot be explained by other factors without much doubt

 Definitely related, sequence of events that is compatible with study related procedure and cannot be explained by other factors beyond a reasonable doubt.

#### 4.Severity or intensity definition.

Severity describes the intensity of a specific event and is not related to whether or not it is a serious adverse event. Severity is defined as:

- Mild: symptoms barely noticeable or does not make the subject uncomfortable.

– Moderate: symptom of sufficient severity to make the subject very uncomfortable.

– Life-threatening: symptom of a sufficient severity to cause the subject to be in immediate risk of death. Treatment for the symptom may be given.

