## 3. Study design

3. A. Specific Aims: In this **pilot** proposal, we will test the feasibility of roflumilast to decrease all cause readmission and mortality 180 days after hospitalization for acute COPD exacerbation. We propose to conduct this study in 100 patients at three centers to assess the tolerance and treatment effect of roflumilast in order to power an appropriate definitive phase III multicenter trial.

Our ultimate specific aims in the **phase III trial** will be to assess: **1**) Primary aim: Evaluate the effects of roflumilast 500 ug daily in hospitalized AECOPD patients on time to all-cause mortality or re-hospitalization during the 180 days following randomization and; **2**) Secondary aims: Evaluate the effects roflumilast 500 ug daily in this population on the following outcomes: respiratory-related death or re-hospitalization during the 180 days following randomization; rate of death or readmission during the 30 days postdischarge; treatment failure (see definition below); change in health status, FEV1, and dyspnea during the 180 days following randomization; post-randomization ICU admission, need for non-invasive or invasive mechanical ventilation, and length of hospital stay during the index hospitalization and; 3) Other: Assess tolerance of roflumilast vs. placebo in hospitalized AECOPD

**3.B. Study Design and Synopsis:** Parallel-group, prospective, randomized, double blind, placebo-controlled trial of roflumilast 500 ug daily vs. placebo in approximately 100 hospitalized AECOPD patients (Figure 3). Both groups will receive GOLD guideline-recommended care.

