## 4. N. Contraindications and side effects to the use of Roflumilast.

**1. Contraindications**: Roflumilast in contraindicated in patients with moderate or severe liver impairment (Child-Pugh class B and C)

2. Side effects: Adverse events experienced by > 3% of patients in clinical trials of roflumilast included diarrhea (9.5%), weight loss (7.5%), nausea (4.7%), headache (4.4%) and back pain (3.2%). Patients discontinued therapy due to adverse effects more frequently with roflumilast (14.8%) compared to placebo (9.9%). Diarrhea and nausea were the most common adverse reactions leading to drug discontinuation in prior trials. Serious adverse events that occurred more frequently with roflumilast compared to placebo included diarrhea, atrial fibrillation, lung cancer, prostate cancer, acute pancreatitis acute renal failure. Less common adverse events, (1-2%) of patients that were more frequently reported with roflumilast use as compared to placebo included abdominal pain, anxiety, heartburn, depression, gastritis, rhinitis, sinusitis, muscle spasms, tremor, urinary tract infection, and vomiting. Roflumilast carries a warning for increased psychiatric adverse events and suicidality. Patient should be monitored for changes in mood including worsening insomnia, anxiety or depression or suicidal ideations. Roflumilast also carries a warning for weight loss. 20% of patients may experience moderate weight loss between 5 to 10% of ideal body weight compared to 7% with placebo.

Roflumilast side effects reported in  $\ge 2\%$  of recipients from 8 clinical trials as listed in the manufacturer's package insert are listed in the table below.

Treated with Roflumilast 500 mcg daily and Greater Than Placebo Treatment		
Adverse Reactions	Roflumilast	Placebo
(Preferred Term)	(N=4438)	(N=4192)
	n (%)	n (%)
Diarrhea	420 (9.5)	113 (2.7)
Weight decreased	331 (7.5)	89 (2.1)
Nausea	209 (4.7)	60 (1.4)
Headache	195 (4.4)	87 (2.1)
Back pain	142 (3.2)	92 (2.2)
Influenza	124 (2.8)	112 (2.7)
Insomnia	105 (2.4)	41 (1.0)
Dizziness	92 (2.1)	45 (1.1)

Decreased appetite	91 (2.1)	15 (0.4)

Other side effects reported in 1- 2% of recipients include: Gastrointestinal disorders (abdominal pain, dyspepsia, gastritis, vomiting); Infections and infestations (rhinitis, sinusitis, urinary tract infection); Musculoskeletal and connective tissue disorders (muscle spasms); Nervous system disorders (tremor); and Psychiatric disorders (anxiety, depression).

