#### 5. Documentation of adverse events.

Any adverse event, serious adverse event, or unanticipated problem occurring during the study must be documented in the subject source documents on the appropriate case report form page. Information relating to the adverse event such as onset, cessation date and times, intensity, seriousness, relationship to study drug and outcome is also documented in the case report form.

All adverse events will be followed until resolution, stabilization or until they are judged by the investigator to be no longer be clinically significant. All serious adverse events will be followed until resolution, stabilization, death, or subject withdrawal. Case report forms will be updated with any new or additional information as appropriate.

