## 4. Q. Assessment of effectiveness.

The present proposal is a pilot study designed to test the feasibility of a future project to be conducted in a multicenter trial in hospitalized patients, to determine the tolerance of roflumilast in hospitalized COPD patients, and to determine the treatment effect of roflumilast to decrease all-cause mortality and all cause readmission rate as add-on therapy. The specifics aims will be:

- 1. Determine the tolerance of roflumilast in hospitalized COPD patients
- 2. Determine the treatment effect of roflumilast as add-on therapy to decrease all cause readmission and mortality as a composite endpoint 180 days after randomization to roflumilast or matching placebo ≤ 12 hours after hospitalization for acute COPD exacerbation.

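### As printed, the adverse-event severity scale has no grade between very uncomfortable and life-threatening, and none for ordinary discomfort, in a pilot that lists tolerance as an aim

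*Combined protocol and SAP*

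**What the plan says.** Section 4.P.4 (Severity or intensity definition) prints three grades in rising order:

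- The lowest grade is given as "Mild: symptoms barely noticeable or does not make the subject uncomfortable".
- The middle grade, next in the list, is given as "Moderate: symptom of sufficient severity to make the subject very uncomfortable".
- The highest grade, which follows directly, is given as "Life-threatening: symptom of a sufficient severity to cause the subject to be in immediate risk of death".

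The same section keeps intensity apart from seriousness: "Severity describes the intensity of a specific event and is not related to whether or not it is a serious adverse event".

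Section 4.P.5 makes intensity a recorded item on the case report form: "Information relating to the adverse event such as onset, cessation date and times, intensity, seriousness, relationship to study drug and outcome is also documented".

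Tolerance is a declared purpose of the pilot. Section 3.A says the 100-patient study is meant "to assess the tolerance and treatment effect of roflumilast in order to power an appropriate definitive phase III multicenter trial". Section 4.Q says the pilot is to "determine the tolerance of roflumilast in hospitalized COPD patients" and lists this first of its two specific aims. Section 4.R.4 includes tolerance of roflumilast against placebo among the outcomes to be compared.

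**The concern.** A severity scale should place every event in exactly one grade. This one leaves two stretches uncovered. Above Moderate, the next step is immediate danger to life, so an event that disables the subject without that danger has no separate place. Below Moderate, plain discomfort is too much for Mild and too little for Moderate.

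Two site investigators could grade the same event differently and both claim to have followed the text. In the upper gap, those who choose Moderate hide the worst non-life-threatening events among lesser ones. Those who choose Life-threatening inflate the top grade. Either way, the intensity data cannot show whether one arm had more severe events than the other. That is a question a sponsor would reasonably ask of a pilot that is meant to report on tolerance before a phase III trial.

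Severity also enters a reporting decision. Section 4.P.2 lists unexpected severity as one way in which an incident can meet the first criterion for an unanticipated problem. A scale with a missing step gives that judgement less to work with.

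**Working it through.** No arithmetic applies and the plan gives no figure to reproduce. The check sets the definitions side by side and looks for anything elsewhere that fills the gaps.

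**Step 1. Run the range of intensity through the printed definitions (4.P.4).**

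| Intensity of the event | Grade under the printed text |
|---|---|
| Barely noticeable, or no discomfort | Mild |
| Uncomfortable, but not very | None fits |
| Very uncomfortable | Moderate |
| Worse than very uncomfortable, no immediate danger to life | No separate grade: Moderate by default, or pushed up |
| Immediate danger to life | Life-threatening |

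Grades defined: 3. Grades between Moderate and Life-threatening: 0. Grades between Mild and Moderate: 0, although the two definitions do not meet.

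**Step 2. Look for another scale that could supply the missing grade.**

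- Section 4.P.1 and the section on reporting serious adverse events to the drug supplier define seriousness.
- Section 4.P.3 and the Causality Assessment section define relatedness.
- The management table in the appendix grades suicidal ideation only.

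None grades adverse-event intensity in general.

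**Step 3. Ask whether seriousness can stand in.** Section 4.P.4 says the two are unrelated. The criteria also differ in content. A subject with disabling diarrhea at home who is not admitted, is in no immediate danger and has no lasting disability may meet no seriousness criterion. The seriousness field would not mark the event, and the intensity field would show Moderate.

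**Step 4. Ask whether the grade is used.** It is a case report form item (4.P.5), and severity enters the unanticipated-problem definition (4.P.2). Section 4.R describes no analysis by grade. Section 4.R.4 compares tolerance between arms without saying how tolerance is measured.

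**The case against.** **The gap may not be in the signed document.** The text was read from a PDF, and a line may have been lost. Plain discomfort is missing just where very uncomfortable is attached to Moderate. A single lost fragment, ending Moderate and opening Severe, would produce both gaps. The closing remark in 4.P.4, that the symptom may be treated, also sits oddly under immediate danger to life. This stands as a caution. Against it, the section shows no redaction or broken table, and its three grades run in order. A slip in drafting explains the text equally well. One look at the source page settles it.

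**Events are not lost.** A reader might infer that severe events go unrecorded. They do not: they can still be entered as Moderate or Life-threatening. Any that lead to admission, longer stay or lasting disability are also captured as serious. What is missing is the subdivision. This stands, and it limits the harm.

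**No planned analysis needs the grade.** This is correct for 4.R. The prior evidence in 4.N is given mainly as incidence and discontinuation, which need no grade. It lowers the weight of the point, but a required field should still be defined so that it can be completed consistently.

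**The link to stopping treatment is tempting but undocumented.** Section 4.N says "Diarrhea and nausea were the most common adverse reactions leading to drug discontinuation in prior trials". A reader might infer that the missing grade is the one that explains stopping. The sentence says which events led to discontinuation, not how severe they were, so the documents do not support that inference.

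**The rates in 4.N do not size the defect.** A reader might also apply the diarrhea or discontinuation percentages in 4.N to the 100 patients. Those are overall rates, and a missing severity grade changes neither.

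**Conclusion.** The point holds for the text as printed. The scale in 4.P.4 has no separate grade for events worse than very uncomfortable but without immediate danger to life, and none for ordinary discomfort. Followed literally, the intensity field pools severe events with moderate ones or overstates them as life-threatening.

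The size is not known. The documents give no rate of severe events, so no number of misgraded events can be stated. The consequence is confined to the description of tolerance and to judgements that rest on severity. The primary outcome in 4.R.2, time to re-hospitalization or death, is unaffected.

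Tolerance comes first in the list in 4.Q, but a reader should not take that to mean it is the primary endpoint. Nor do the lists in 3.A and the Outcomes section that place tolerance under Other demote it here, because they describe the later phase III trial.

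The conclusion rests on one assumption: that the source page reads as the extracted text does. If a Severe line is there, the upper gap disappears, and the lower one should be judged from the same page. If not, the change is worth making because it is cheap and bears on a stated aim.

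**What to change.** 1. Check 4.P.4 on the source page, and the intensity codes on the case report form.
2. If no Severe grade is there, add one between Moderate and Life-threatening. It could cover, for example, an event that prevents usual activity but carries no immediate danger to life.
3. Reword Mild and Moderate so that ordinary discomfort falls in one of them and adjacent grades meet.
4. Add the matching code to the case report form.
5. If enrolment has begun, re-grade earlier events from source documents without knowledge of treatment arm. Include Moderate and Life-threatening events for the upper gap, and Mild and Moderate events for the lower one.

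The cost is a short amendment to one definition and one form code. Re-grading adds some site work and has a small downside: 4.P.5 does not name functional impact among the items to record, so some earlier events may lack the information needed. Those should be marked as not re-gradable rather than assigned from memory.

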#### 5. Documentation of adverse events.

Any adverse event, serious adverse event, or unanticipated problem occurring during the study must be documented in the subject source documents on the appropriate case report form page. Information relating to the adverse event such as onset, cessation date and times, intensity, seriousness, relationship to study drug and outcome is also documented in the case report form.

All adverse events will be followed until resolution, stabilization or until they are judged by the investigator to be no longer be clinically significant. All serious adverse events will be followed until resolution, stabilization, death, or subject withdrawal. Case report forms will be updated with any new or additional information as appropriate.

## 6. Reporting responsibilities of the investigator.

All serious adverse events, regardless of expectedness or causality will be reported by the site immediately (no later than 24 hours after occurrence to the sponsor, Temple IRB in accordance with IRB regulations and guidelines of the Temple IRB.

# Reporting of Serious Adverse Events to Forest Research Institute (FRI) Serious Adverse Event (SAE)

A serious adverse event is one that:

- Results in death
- Is an immediate threat to life
- Requires inpatient hospitalization, or prolongation of existing hospitalization
- Results in persistent or significant disability/incapacity
- Is a congenital anomaly or birth defect.

#### Causality Assessment

For all AEs, the Investigator must provide an assessment of causal relationship to the IP. Causal relationship must be assessed by answering the following question:

Is there a reasonable possibility the IP caused the event?

- Yes: There is evidence to suggest a causal relationship between the drug and the adverse event (ie, there is a reasonable temporal relationship, and/or the events are unlikely to be attributable to underlying disease, other drugs, or other factors). Dechallenge and/or rechallenge (if available) is positive
- No: The relationship is unlikely or nonexistent (ie, there is no reasonable temporal relationship and/or the events are likely to be manifestations of underlying diseases, or commonly occur in the study population independent of drug exposure or other drugs/factors provide plausible explanations for the events), or the patient did not take the investigational product.

The Sponsor (Principal Investigator) is required to inform Forest Global Drug Safety of all SAEs. Forest Global Drug Safety must be notified immediately regarding any SAE that occurs after informed consent is obtained.

The Principal Investigator must report the event within 24 hours of first knowledge of any AE that meets one of the criteria for an SAE, to Forest Global Drug Safety on an SAE report form. If, during follow-up, any non-serious AE worsens and eventually meets the criteria for an SAE, that AE should be recorded as a new SAE.

The study center must transmit the SAE report form to the SAE [contact] within 24 hours of first awareness of the event at the study center.

Supplemental information shall be submitted as soon as available and may include laboratory results, radiology reports, progress notes, hospital admission and emergency room notes, holding and observation notes, discharge summaries, autopsy reports, and death certificates.

## Reporting of Pregnancy to Forest Research Institute

Study center personnel must report every pregnancy on a pregnancy report form as soon as possible (within 24 hours of first awareness of the pregnancy to the pregnancy fax number, **[contact]**), even if no AE has occurred, and follow it to term. If, however, the pregnancy is associated with an SAE (eg, if the mother is hospitalized for dehydration), in addition to the pregnancy report form, a separate SAE report form must be filed.

Fax all relevant SAE or pregnancy information to Forest Global Drug Safety. Contact information for Forest Global Drug Safety, personnel is as follows:

FOREST GLOBAL DRUG SAFETY DEPARTMENT [contact]

## 4. Q. Assessment of effectiveness.

The present proposal is a pilot study designed to test the feasibility of a future project to be conducted in a multicenter trial in hospitalized patients, to determine the tolerance of roflumilast in hospitalized COPD patients, and to determine the treatment effect of roflumilast to decrease all-cause mortality and all cause readmission rate as add-on therapy. The specifics aims will be:

- 1. Determine the tolerance of roflumilast in hospitalized COPD patients
- 2. Determine the treatment effect of roflumilast as add-on therapy to decrease all cause readmission and mortality as a composite endpoint 180 days after randomization to roflumilast or matching placebo ≤ 12 hours after hospitalization for acute COPD exacerbation.

## 4. R. Statistical analysis plan.

The primary analysis for all study outcomes will be performed on an intention to treat basis. In the intention to treat approach, all subjects are analyzed in the group to which they were randomized, regardless of whether the assigned treatment was adhered to and regardless of whether there were any eligibility violations.

## 1. Analysis of baseline characteristics.

Univariate descriptive statistics will be calculated for baseline parameters overall and by treatment group. For categorical outcomes, these will include the number percentage of subjects in each category. For continuous variables, these will include the mean and standard deviation for variables with approximately normal distributions and the median and 25th and 75% percentiles for variables with skewed distributions.

**2.** Analysis of the primary endpoint. The primary outcome is time from randomization to a composite outcome of all cause re-hospitalization and all-cause mortality, whichever comes first. The primary analysis will be a log-ranked test and associated Kaplan-Meier plot, unadjusted for any covariates. Censoring will occur at the earliest date of any of the following occurrences, unless the subject has already experienced the primary outcome event:

• Lost to follow-up despite intensive efforts

- Subject or healthcare proxy withdrawal of consent
- 180 days after randomization.

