## Table1. Readmission rates following COPD Hospitalization

Dinesen et al 2012	Prospective	~5%	~6%	~10%

The rate of 30 day readmissions in these reports varies from 5-34% with the majority of studies suggesting that approximately 15% suffer such an event in that time frame. This readmission rate increases further by 60 days (6-30%) and 90 days (10-40%).Data from the AHRQ using the HCUP database found that 20.5% of U.S. COPD patients were readmitted within 30 days and that 85% of these included COPD as the primary or secondary diagnosis).{{1159 Elixhauser,A. 2011}} A summary of published literature suggests that readmissions are frequently seen in this population.

Survival is another extremely relevant endpoint to study the effect of an intervention during COPD hospitalization. The Study to Understand Prognosis and Preferences for Outcomes and Rates of Treatment (SUPPORT enrolled patients admitted with COPD exacerbations and reported an in-hospital mortality of 11% in patients presenting with acute hypercapneic respiratory failure.{{1152 Connors,A.F.,Jr 1996}} The 180 day mortality was 33% and the 2-year mortality was 49%. Several

other studies have reported in-hospital mortality rates of 11-24% and 22-35% after one and two year's follow-up respectively (Figure 2). The 2010 PHC4 dataset reports the average inpatient mortality rate for COPD readmissions to be 3.9%, but ranges from non-complicated readmission mortality rates of 1.45 % to 5.0% if pneumonia is the cause of readmission in a patient initially admitted with COPD or even higher at 11.6% mortality if respiratory failure is the cause for readmission.

These data demonstrate that readmission and survival following COPD hospitalization are clinical relevant and meaningful endpoints that occur with increased frequency following the index hospitalization.

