## 4. B. Study Procedure

Study will begin before patient's discharge from the hospital and last for 194 days.

Baseline: Will occur during the duration of admission stay in the hospital. Patients will have a medical history taken as well as smoking history. Patients will also be given a physical exam including vital signs. A spirometry test will also be performed. Women with the potential to become pregnant will be given a pregnancy test. Data will also be collected in regards to dyspnea scales, Deyo-Charlson index, and GOLD classification. Patients will complete a Columbia Suicide Severity Rating Scale to exclude patients with a history of suicidal behavior  $\leq 2$  years or suicidal ideation  $\leq 6$  months prior to enrollment Randomization: Patients who are eligible to enroll in this study will be randomized to one of two treatment groups. Randomization will be done using a randomized block design stratified by treatment center. One group will receive rollumilast 500 mcg (Daliresp®) and the other will receive a placebo tablet. Patients will begin one of these treatment arms prior to hospital discharge for a total period of 180 days post enrollment.

Day of hospital discharge: A spirometry test will be performed and an adverse event assessment will be completed.

Day 7: Phone Visit. Data to be collected includes: interim history, adverse events assessments, vital status, and exacerbation history. During this telephone visit the study doctor or nurse coordinator will ask how the patient is feeling and if they have needed to visit the doctor or go to the emergency room or hospital since the last time they were contacted. They will be asked how well they are tolerating the study drug.

Day 14: Clinic Visit. At this visit vital signs, C-SSRS test, interim history, adverse event assessment, vital status, and exacerbation history will be recorded. The following questionnaires will given: EQ-5D, the St. George's Respiratory Questionnaire (SGRQ), and the Modified Medical Research Council dyspnea score (MMRC).

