## 3. Analysis of secondary outcomes.

Primary analysis of other time to event outcomes will be performed using unadjusted log rank tests that have associated Kaplan-Meier plots, similar to the primary analysis of the primary study outcome. Secondary analysis of these outcomes will use Cox regression to adjust for baseline subject factors (covariates) that are known to be associated with the outcome.

The primary analyses of changes in continuous measures such as absolute and percent changes in spirometry and dyspnea scores, for example, will be analyzed using an analysis of covariance where change from baseline to a particular time period is the dependent variable.

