## 4. Assessment of treatment effect

In this pilot proposal, the treatment effect of roflumilast vs. placebo to prolong the time to event of a combined endpoint of death or re-hospitalization will be assessed in an intention to treat manner. In a similar manner, the treatment effect of roflumilast vs. placebo to effect all of the secondary endpoints proposed to be measured in the pivotal phase III trial will also be measured (time to respiratory death or respiratory re-hospitalization during the 180 days post-randomization; rate of death or readmission at 30 days post-discharge; treatment failure [see definition below]; change in health status, change in FEV1, and dyspnea during the 180 days post-randomization; length of hospital stay during the index hospitalization; and the tolerance of roflumilast vs. placebo in hospitalized AECOPD).

Because this is a pilot study the intent is to see if there is a signal that would justify a larger clinical trial. Therefore the significance level has been set to 0.1 and the power has been set at 0.7. A total of 100 patients will enter this two treatment parallel-design study. The probability is 70 percent that the study will detect a treatment difference at a two sided 10.0 percent significance level, if the true hazard ratio is 1.654. This is based on the assumption that the accrual period will be 36 months and the follow up period will be 6 months and the median time to event is 8 months. The total number of events will be 73.

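### Randomisation is stratified by center, but the primary log-rank test ignores center and no hazard ratio with interval is specified for the primary endpoint

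*Combined protocol and SAP*

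**What the plan says.** Randomisation (Section 4.B): "Randomization will be done using a randomized block design stratified by treatment center".

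Primary endpoint, time to first re-hospitalisation or death (Section 4.R.2): "The primary analysis will be a log-ranked test and associated Kaplan-Meier plot, unadjusted for any covariates". Follow-up is censored at 180 days.

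Other endpoints (Section 4.R.3): "Primary analysis of other time to event outcomes will be performed using unadjusted log rank tests", and then "Secondary analysis of these outcomes will use Cox regression to adjust for baseline subject factors". The factors are not listed, center is not mentioned, and no interval is named.

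Purpose: Section 4.Q lists as an aim "Determine the treatment effect of roflumilast as add-on therapy to decrease all cause readmission and mortality as a composite endpoint". Sections 3.A and 3.B (Outcomes) say that the pilot's effect estimate will be used to power a phase III trial. Section 4.R.4 adds that "the intent is to see if there is a signal that would justify a larger clinical trial", and sets a two-sided 10% level and 70% power "if the true hazard ratio is 1.654". That design value is the only hazard ratio in the plan.

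**The concern.** Two things are missing from the primary analysis.

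The first is center. Stratified blocking balances the arms within each center. If event risk differs between centers, the treatment comparison then varies less from trial to trial than an analysis that pools the centers assumes. The pooled log-rank test therefore rejects less often than its nominal level and gives up some power. The level was relaxed to 10% so that a signal would be easier to see, and a test that runs below 10% gives part of that back.

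The second is the estimate. A log-rank p-value and a Kaplan-Meier plot do not quantify an effect for phase III planning. An approximate hazard ratio can be recovered from the log-rank quantities, but its model, direction and interval level are not fixed in advance.

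**Working it through.** **The plan's own figure.** The inputs from Section 4.R.4 are a hazard ratio of 1.654, two-sided alpha 0.10 and power 0.70. Equal allocation is my assumption. Schoenfeld's formula gives 4 x (1.645 + 0.524)^2 / (ln 1.654)^2 = 74.3 events, against 73 stated. Power at 73 events is 0.693. With uniform 36-month accrual, follow-up to study end and exponential times, taking 8 months as the placebo median gives 74.5 events. Taking it as the roflumilast median gives 86.8. The placebo reading fits the stated 73 better and is the main case below.

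**Events under the censoring in 4.R.2.** The cap is 180/30.44 = 5.91 months.
- 8 months as placebo median: event probabilities 0.401 (placebo) and 0.266 (roflumilast), so 50 x (0.401 + 0.266) = 33.4 events.
- 8 months as roflumilast median: 50 x (0.572 + 0.401) = 48.6 events.

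**Stratified against unadjusted test.** The documents give no center sizes or event rates, so those are assumptions. I simulated 100 patients with near-equal arms within center, exponential times, the 5.91-month cap and a two-sided 10% test. The placebo median is 8 months at the weighted geometric mean of the center hazards. Three centers of 40/30/30 have log-hazard steps of 0, 0.3, 0.5 or 0.7 between adjacent centers, so the highest-to-lowest ratio is exp(2 x step). There were 40,000 trials per row, with both tests run on the same data.

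| Hazard spread | Mean events | Power, unadjusted | Power, stratified | Alpha, unadjusted | Alpha, stratified |
|---|---|---|---|---|---|
| equal | 33.4 | 0.421 | 0.420 | 0.101 | 0.101 |
| 1.8-fold | 33.8 | 0.418 | 0.425 | 0.095 | 0.100 |
| 2.7-fold | 34.6 | 0.409 | 0.430 | 0.087 | 0.099 |
| 4.1-fold (extreme) | 35.7 | 0.393 | 0.439 | 0.078 | 0.102 |

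The Monte Carlo standard error of the paired gain is 0.07 to 0.12 points.

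**Variations** (20,000 trials each, standard error at most 0.19 points).
- One dominant center (70/16/14): gains of 0.4 to 0.6 points at 1.8-fold and 1.0 to 2.2 at 2.7-fold, depending on where that center sits in the risk order.
- 8 months as roflumilast median, 40/30/30: -0.2, +1.1 and +3.6 points at equal, 1.8-fold and 2.7-fold.
- Cost when centers are alike: 0.1 points at 40/30/30, 0.3 at 70/16/14, 0.2 at 86/12/2, 0.3 at 90/6/4, and 0.3 to 0.4 with four strata.

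**Different split.** With 50/30/20, blocks of 4, hazard multipliers of 1.5/1/0.67 and the same 180-day cap (10,000 trials), power is 0.442 against 0.452 and alpha 0.098 against 0.105. The pattern is the same.

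**Width of the missing interval.** With SE(log HR) about 2/sqrt(d), the 90% CI is exp(ln 1.654 +/- 1.645 x 2/sqrt(d)).
- d = 34: 0.94 to 2.91 (p = 0.14)
- d = 49: 1.03 to 2.65
- d = 73: 1.13 to 2.43

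**Direction.** 1/1.654 = 0.605. Section 4.R.4 does not say which arm is the reference.

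**The case against.** The best defence is that the unadjusted test is pre-specified and valid, and that every gain above rests on an assumed spread between centers. The documents lean toward a small one. Section 4.J gives all patients standardised care, Section 5 makes Temple the recruitment anchor, and the site description has Episcopal inpatients transferred to the main campus. Section 4.R.4 also commits to assessing the effect on the composite and frames the design as a hazard ratio, so the effect aim is not abandoned. All of this stands and limits the size of the point. It does not supply the missing specification. Even if the Cox sentence in 4.R.3 were read to cover the primary endpoint, it names neither center nor an interval.

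Four stronger readings are tempting, and the documents do not support them.
- *The test is invalid or its type I error is inflated.* Any departure from the nominal level is in the conservative direction.
- *The published readmission ranges show how far these centers may differ.* Section 1.B gives 5-34% at 30 days, 6-30% at 60 and 10-40% at 90. Under constant hazards these imply ln(0.66)/ln(0.95) = 8.1-fold, ln(0.70)/ln(0.94) = 5.8-fold and ln(0.60)/ln(0.90) = 4.8-fold. They are differences between published studies. They neither estimate nor bound the spread among these hospitals.
- *Ignoring center would bias the hazard ratio enough to mislead phase III.* The simulated median is 1.65 against 1.66 at 1.8-fold and 1.63 against 1.66 at 2.7-fold. A shift of 0.01 to 0.03 is negligible beside an interval of 0.94 to 2.91.
- *The loss is large.* A loss of 18 points (0.52 against 0.70) can be produced, but only with a 6.25-fold spread and follow-up to study end, which 4.R.2 rules out. Power near 0.42 comes from 33 to 36 events where 73 were planned. That is a separate matter, and stratifying does not cure it.

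**Conclusion.** The point holds as a small efficiency and alignment improvement. The primary test does not follow the randomisation strata, and the primary endpoint has no pre-specified hazard ratio or interval. The first gap has an unknown effect, probably 0 to 2 power points under 180-day censoring with 8 months as the placebo median. It could be somewhat more if 8 months is the roflumilast median and centers differ markedly. These sizes rest on assumed center sizes, assumed hazard spreads, exponential times and equal allocation. The second gap needs no assumption about centers and bears more directly on a stated aim, since phase III planners need to see both the estimate and how wide its interval is. Neither gap invalidates the planned test.

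**What to change.** In Section 4.R.2:
1. Make the primary log-rank test stratified by the randomisation center variable, with strata taken from the randomisation list. Keep the unadjusted log-rank as a sensitivity analysis.
2. Report with it the hazard ratio from a Cox model stratified by the same variable, with a 90% CI to match the two-sided 10% level. State the direction, because 1.654 is 0.605 the other way round.
3. Define the strata. Section 3.A speaks of three centers and Section 4.A names four hospitals. Part of the site description was not available to me, so I do not judge how many there should be.

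This takes two or three sentences and no new data. The downside is a few tenths of a power point if centers do not differ, at most about 0.4 in the 180-day scenarios, including very unequal splits and four strata. Under follow-up to study end, which 4.R.2 does not allow, the equal-center cost at 50/30/20 was 1.6 points (0.697 against 0.681).
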